5.6 Patient management during treatment

All patients will be seen one time by the radiation oncologist during treatment. Radiation reactions will be recorded with attention toward the following:

- a) Rectal or small bowel symptomatology (cramping, diarrhea, rectal urgency, hematochezia)
- b) Bladder symptomatology (frequency, urgency, nocturia, dysuria)
- c) Radiation dermatitis
- d) Side effects will be treated based on the discretion of the radiation oncologist, and documentation kept in the medical record. Rectal side effects such as diarrhea may be treated with diphenoxylate or loperamide. Bladder or rectal spasms can be treated with anticholinergic agents or tolterodine. Irritative or obstructive voiding symptoms can be managed with alpha-blockers or phenazopyridine.

6.0 PATIENT ASSESSMENTS

6.1 Study Parameters

- H&P – at initial consult and following treatment protocol
- PSA – At baseline, 3 and 6 months after treatment, then every 6 months until 3 years, and then annually until year 5
- Testosterone – At baseline, 3 and 6 months after treatment, then every 6 months until 3 years, and then annually until year 5
- Bone Scan - at baseline*
- Pelvic CT or other lymph node assessment - at baseline*
- Symptom assessment (IPSS, SHIM, modified EPIC sheet, as per Appendix I) – At baseline, 3 and 6 months after treatment, then every 6 months until 3 years, and then annually until year 5
- Serum ALT, AST and AP at baseline and one month following initiation of ADT.
- Optional Blood draw collected at baseline and at 3 and 24 months following treatment completion. Patients who have initiated ADT prior to consent for optional blood samples will be ineligible to give extra blood samples.
- Seed placement of at least 3 gold seeds at least 1 week prior to first CT simulation if additional image guidance is not being used
- CT simulation will occur prior to radiation treatment as standard of care and then again during radiation any time after fraction 3 as a QA procedure for monitoring prostate rotation in relation to seed placement. However, second CT simulation after fraction 3 is only necessary if patient had fiducial placement.

* CT/MRI and Bone scan optional except for the patients who are:

1. Gleason 4+3
2. >50% cores positive
3. >1 intermediate risk factor (GS 7, PSA ≥ 10 and T2b-T2c).

Safety run-in phase

A phase I trial of SBRT in prostate cancer (n=45) composed of 60% intermediate-risk, localized patients where 22% of men were treated with androgen deprivation has been recently reported (ref. 7). This trial used considerably higher SBRT doses than our current trial (9-10 Gy x5 versus 7.25 Gy x5) and still reported no Grade 3 or 4 GI or GU acute toxicities (<90 days). Therefore, we believe our more modest SBRT fractionation scheme of 7.25 Gy x5 is likely safe in combination with androgen deprivation. To ensure that this combination is safe, the first six patients will be treated and analyzed for toxicity for 3

months after radiation. Six patients will be enrolled at the proposed dose of SBRT and androgen deprivation therapy and if 0 or 1 patient experiences a dose limiting toxicity (DLT) then this regimen will be considered safe (note: accrual will continue while the interim analysis is being conducted). If >1 patient experiences a DLT than this regimen will be considered unsafe and the trial will stop at this point. DLT for the purpose of calculation of the maximum tolerated dose (MTD) includes medically unmanageable Grade 3 or any Grade 4 toxicity with an *attribution* of probably related to protocol intervention (see section 10.2).

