9.0 ACCRUAL AND STUDY DURATION

Of approximately 90 patients per month seen in consultation for prostate cancer each month in the department of radiation oncology (East Baltimore, Green Spring Station, Sibley and Suburban sites total), we anticipate approximately 25% of patients to be eligible. All eligible patients will be offered enrollment on the study, and we estimate a 30% accrual rate with 5% dropout rate, resulting in an average of at least 7 patients enrolled per month. The planned study open date is June 2013 for the East Baltimore site and May 2014 for Sibley and Suburban sites. The projected closure date of accrual is August 2015. The total length of the study would be from June 2013-August 2020.

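### The safety run-in decides from the first six men only while accrual stays open, so about 6 to 21 further irradiated men are outside its rule when it reads out

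*Combined protocol and SAP*

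**What the plan says.** The safety run-in is described at the end of protocol section 6.1. Its purpose and cohort are given together: "To ensure that this combination is safe, the first six patients will be treated and analyzed for toxicity for 3" months after radiation.

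The decision rule has two branches. On the favourable side, "if 0 or 1 patient experiences a dose limiting toxicity (DLT) then this regimen will be considered safe". On the other, "If >1 patient experiences a DLT than this regimen will be considered unsafe and the trial will stop at this point". A DLT is a medically unmanageable grade 3 toxicity or any grade 4 toxicity, probably related to the intervention. It is not limited to GU or GI events.

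The favourable branch carries the remark "note: accrual will continue while the interim analysis is being conducted". No pause or enrolment cap is stated anywhere.

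Other relevant provisions:
- **Section 8.4** counts probably related grade 3 or higher GU or GI toxicity in all patients. It looks first at 50 recruited, where 12 or more stops the trial, and again at 100.
- **Section 9.0** plans accrual "resulting in an average of at least 7 patients enrolled per month". This rests on consultations summed over East Baltimore, Green Spring Station, Sibley and Suburban. East Baltimore opens in June 2013, and Sibley and Suburban in May 2014.
- **Section 16.0** has all adverse events, across sites, reviewed at semimonthly teleconferences with an impartial physician monitor.
- **Section 7.0 (calendar)** marks toxicity assessment before treatment, during radiation, and next at 3 months. Nothing is marked at 1 or 2 months, yet footnote 16 gives visit windows for both. Section 6.2.1 starts follow-up at 3 months.

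**The concern.** A run-in normally either limits exposure until the first men have been observed, or bases its decision on all the evidence available at that time. This one does neither. Accrual stays open, and the denominator is fixed at six. With one DLT in the six the regimen passes, whatever has been seen in man seven onward.

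Six men carry little information. If the true DLT rate is worrying, the rule will often pass the regimen while further DLTs are already on file in men it does not count. The first formal safety conclusion would then rest on a minority of the irradiated men, or at best half of them. The next numeric rule comes later and covers a different set of events.

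**Working it through.** **Inputs.** Six men, 3 months of observation after radiation, 0 or 1 DLT to pass (section 6.1). Radiation over 2 weeks, taken as 0.5 month (section 5.0). ADT for 4 months, starting at least 1 month before radiation (section 5.5). Accrual rate and site dates (section 9.0). Total of 110 men (section 8.3).

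**The plan's accrual rate.** 90 × 0.25 × 0.30 = 6.75 per month, which rounds to the stated 7. With the stated 5% dropout, 6.75 × 0.95 = 6.41. Enrolling 110 men over the roughly 26 months from June 2013 to August 2015 implies 110/26 = 4.2 per month. The documents give no rate for the period before Sibley and Suburban open; I assume 2 to 3.5 per month.

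**Men irradiated by the read-out.** Assume constant accrual r, ADT starting at enrolment, and a lead-in of L months. The sixth man enrols at 6/r and reads out at 6/r + L + 0.5 + 3. A man has finished radiation by then if he enrolled at least L + 0.5 months earlier, so the count is r × (6/r + 3) = 6 + 3r. The lead-in cancels.

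| r per month | Read-out (L = 1), months | Enrolled | Radiation finished | Outside the six |
|---|---|---|---|---|
| 7 | 5.4 | 37.5 | 27 | 21 |
| 6.41 | 5.4 | 35 | 25 | 19 |
| 4.2 | 5.9 | 25 | 19 | 13 |
| 3.5 | 6.2 | 22 | 16.5 | 10.5 |
| 2 | 7.5 | 15 | 12 | 6 |

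With Poisson accrual at 7 per month, the 95% range for radiation finished is about 19 to 36.

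Far fewer have finished both radiation and 4 months of ADT. At 7 per month the count is r × (read-out − 4): 7 × 1.36 = 9.5 with a 1-month lead-in, and 7 × 2.36 = 16.5 with 2 months.

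**The six-man rule.** P(2 or more DLTs in 6) is 3% at a true rate of 5%, 11% at 10%, 34% at 20% and 58% at 30%. At 20%, 21 × 0.20 = 4.2 DLTs would be expected among 21 uncounted men once fully observed.

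**The section 8.4 look.** Fifty men are recruited after 50/7 = 7.1 months, 50/4.2 = about 12 months, or 50/2 = 25 months. P(12 or more of 50) at a true 20% rate is 29%, even if all 50 are fully observed.

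**Adding a pooled check.** Trigger if there are 2 or more DLTs in the six, or if the proportion among all irradiated men exceeds 1 in 6. The second condition means at least 3 of 12, 3 of 16, 4 of 19 or 5 of 27. Treating every man as fully observed:

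| True DLT rate | Six only | n = 12 | n = 16 | n = 19 | n = 27 |
|---|---|---|---|---|---|
| 5% | 3% | 4% | 6% | 4% | 4% |
| 10% | 11% | 16% | 25% | 18% | 20% |
| 20% | 34% | 51% | 67% | 61% | 70% |

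These are upper limits. At the read-out the sixth man is the last with a full 3-month window. Every added man has less, about 1.5 months on average.

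**The case against.** The strongest reply is that later men are not unprotected. Their probably related grade 3 or higher GU and GI events enter the section 8.4 boundary, whose threshold is lower than the DLT definition. All adverse events are reviewed semimonthly. Fatal events and serious unanticipated events must reach the Coordinating Center within 24 hours (section 16.0). The principal investigator must confirm that safety outcomes favour continuing (section 18.0). This stands. A reader might infer that DLTs after the sixth man count nowhere, and the documents do not support that. They are absent from the run-in rule only. What remains is that the ongoing reviews carry no decision criterion, section 8.4 acts only at 50 recruited, and a DLT outside GU and GI in a later man enters no numeric rule.

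Second, a reader might infer that about 27 men have completed the regimen by the read-out. That is too strong. The 27 have finished radiation and include the judged six. They also depend on a four-site rate at a time when two of those sites are not planned to be open.

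Third, open accrual is disclosed and argued for. Section 6.1 cites a trial at higher SBRT doses with no grade 3 or 4 acute GI or GU toxicity. That is a fair reason not to pause, but not a reason to leave DLTs already recorded out of the decision. The remark on accrual might cover only the analysis itself, but no pause is stated for the observation period either.

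Fourth, one might read the rule as waiting for the 3-month analysis even after a second DLT. The stopping sentence does not say so and can be read as taking effect at once.

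Fifth, adverse events are recorded throughout (section 10.1), so an acute DLT can be captured without a 1- or 2-month visit. This makes the calendar a matter of consistency, not a hole in safety reporting.

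**Conclusion.** The point holds in limited form. The run-in decision uses six men, while about 12 to 27 will have finished radiation when it is made, so about 6 to 21 are outside the rule. The lower part of that range, about 12 to 19 irradiated, is more plausible for the run-in period. Even at 12, half the irradiated men are left out.

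The gap is one of unused evidence, not absent oversight. Counting DLTs already in hand could raise detection at a true 20% rate from 34% to at most 51-70%. The true gain is smaller, because none of the added men has a full window.

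This rests on constant accrual, ADT starting at enrolment, and open accrual through the observation period. The rates of 2 to 3.5 per month are assumed. The 6 + 3r count does not depend on the ADT lead-in. It is an inexpensive improvement worth making, not a flaw that invalidates the safety plan.

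**What to change.** Keep accrual open and keep the six-man rule. Add to the run-in text of section 6.1:

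1. At the read-out, DLTs in every man irradiated by that date are tabulated, each man with his follow-up time.
2. If the pooled proportion exceeds the 1 in 6 that the rule already tolerates, the regimen is not declared safe until the Safety Monitoring Committee has reviewed the data. This triggers a review, not an automatic stop.

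Separately, reconcile the calendar's toxicity row, footnote 16 and section 6.2.1 on the 1- and 2-month appointments, so that acute toxicity is recorded at any such contact that takes place.

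The cost is a few sentences of protocol wording, the calendar reconciliation and possibly one extra committee review. There are two downsides. All the added men have less than 3 months of observation, so a reassuring pooled proportion should be read with caution. At a true DLT rate of 10%, the chance of a stop or review rises from 11% to about 16-25%.

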6.2 Follow-up Schedule

6.2.1 Patients will be assessed at three months and at six months after treatment, then every 6 months until 3 years, then annually until year 5. The patient will be off study after 5 years.

6.2.2 Patients who develop a rise in PSA of greater than 25% and of at least 0.3 ng/ml compared to the prior PSA will have PSA drawn every 3 months until PSA either returns to nadir value or rises to a value 2 ng/ml or more above the nadir. The nadir PSA is defined as the lowest PSA value after initiation of treatment. Time of failure will be the date of the first PSA that is 2 ng/ml or more above the nadir.

6.2.3 At any point in time, patients may undergo biopsy for histopathologic assessment of disease response, if there is evidence of recurrence.

7.0 STUDY CALENDAR

	Pre-treatment	Radiation ¹⁴	Follow-Up ¹⁶ (in time post radiation treatment)										
			1 mo	2 mo	3 mo	6 mo	12 mo	18 mo	24 mo	30 mo	36 mo	Year 4	Year 5
Initial Consult	X												
Consent	X												
History and Physical	X				X	X	X	X	X	X	X	X	X
Digital Rectal Exam¹⁵	X				X	X	X	X	X	X	X	X	X
Biopsy¹²													
Histological Diagnosis¹	X												
MRI *	X ³												
Pelvic CT scan *	X ³												
Bone scan *	X ⁴												
Cardiovascular risk assessment	X ⁵												
Quality of Life measures⁶	X				X	X	X	X	X	X	X	X	X
Toxicity assessment⁹	X	X			X	X	X	X	X	X	X	X	X
Biomarker blood draw (optional)	X				X				X				
Serum ALT, AST, and AP¹⁰	X												
Seed placement⁷	X												
CT Simulation¹⁷	X	X											
PSA¹¹	X ²				X	X	X	X	X	X	X	X	X
Testosterone	X				X	X	X	X	X	X	X	X	X
LHRH agonist¹³	X	X	X	X									
Bicalutamide⁸	X	X	X	X									

¹Histological diagnosis and Gleason score provided on the pathology report. All patients, per institutional policy, will have pathology reviewed at Johns Hopkins

²PSA within 4 months prior to registration

³CT scan or MRI of the pelvis within 6 months prior to registration. Lymph nodes evaluated negative by imaging methods will be classified as NX. Only nodes evaluated negative by surgical sampling will be classified as N0.

⁴Bone scan within 2 months prior to registration

⁵Cardiovascular risk assessment if the patient is determined to be "high risk" for vascular event – prior MI or stroke within 5 years

⁶IPSS (less than 16 or patient is excluded from trial participation), SHIM, and modified EPIC bowel questionnaires

⁷At least 1 week prior to simulation, patients will undergo transrectal or transperineal inserting of at least 3 gold seeds to improve accuracy in daily prostate alignment and decrease residual positioning errors. However, if additional image guidance is being used, fiducials will be optional.

⁸At least two weeks of bicalutamide at the initiation of hormone therapy and may be continued through the duration of radiation at the physician's discretion.

⁹Patients will be seen one time by the radiation oncologist during treatment

¹⁰Serum ALT, AST and AP collected before the initiation of ADT and one month (+/- 14 days) following initiation of ADT

¹¹Patients who develop a rise in PSA of greater than 25% and of at least 0.3 ng/ml compared to prior PSA will have PSA drawn every 3 months until PSA either returns to nadir value or rises to a value 2 ng/ml or more above the nadir. The nadir PSA is defined as the lowest PSA value after initiation of treatment. Time of failure will be the date of the first PSA that is 2 ng/ml or more above the nadir.

¹²At any point in time, patients may undergo biopsy for histopathologic assessment of disease response, if there is evidence of recurrence.

¹³Androgen deprivation therapy will be given for 4 months total, (must be given \geq 1 month prior to the start of radiation therapy)

¹⁴Radiation will be given in 5 fractions over 2 weeks (treatment to be performed every other day)

¹⁵Rectal exam is required at baseline. During follow-up it is at the discretion of the treating physician

PI: [name]

IRB00079078

December 20, 2021

¹⁶ Follow-up appointments for 1 month, 2 months, and 3 months have a +/- 7 day tolerance window and all other follow-up appointments have a +/- 30 day tolerance window.

¹⁷ CT simulation will occur prior to radiation therapy and then again during radiation therapy as a QA procedure after fraction 3 only if patients had fiducial placement.

*CT/MRI and bone scan optional except for the patients who are:

1. Gleason 4+3
2. >50% cores positive
3. >1 intermediate risk factor (GS 7, PSA ≥ 10 and T2b-T2c).

8.0 DATA ANALYSIS AND SPECIAL CONSIDERATIONS

8.1 Primary Analysis:

The primary objective is to estimate the 5-year biochemical failure free rate (BFFR) associated with the combined hypofractionated dose regimen and ADT. The BFFR is defined as a binary indicator whether PSA has increased by 2 ng/ml or more above the nadir PSA any time before the end of 5 years. The primary analysis will be performed by first obtaining the Kaplan-Meier (K-M) estimate of the biochemical failure free survival, and then estimating the 5-year biochemical failure free rate (BFFR) from this K-M curve together with 95% confidence interval. Greenwood formula will be used to calculate the variance of K-M estimate.

8.2 Secondary objectives:

8.2.1. Assess the incidence of grade 3 or greater late GU and GI toxicity and self-reported quality of life data.

Kaplan-Meier estimate of the incidence of grade 3 or greater late GU and GI toxicity will be constructed together with 95% confidence interval. Patient reported quality of life will be summarized using means and standard deviation for continuous measures, the contingency tables for categorical measures.

8.2.2 Assess clinical and pathologic control rates associated with the combined hypofractionated dose regimen and ADT.

Assessments will be performed 3 and 6 months after treatment and then every 6 months until 3 years, then annually until year 5. These rates will be estimated from Kaplan-Meier curves together with 95% confidence intervals.

Disease-Free Survival, measured from the date of enrollment to the date of documented progression or date of death using Kaplan-Meier estimates. Progression will be documented by PSA, bone scan, or biopsies.

Time to Local Progression (TLP) will be measured from the date of enrollment to the date of documented local progression using Kaplan-Meier estimates. Patients with new palpable abnormality on digital rectal examination or PSA failure at any point in time will also be offered biopsy to distinguish between local and distant failures. Patients who do not undergo biopsy will be censored at the last point of time they were considered locally controlled by digital rectal examination and PSA and considered not evaluable for further assessment.

Time to Distant Failure (TDF) will be measured from the date of enrollment to the date of documented metastatic disease. Patients who have negative biopsy following PSA failure or palpable abnormality will be considered to have only distant failure.

Overall survival (OS), measured from date of enrollment to date of death using Kaplan-Meier estimates. Every effort will be made to document the cause of death.

8.2.3 Collect dose/volume and imaging data to allow normal tissue complication probability modeling and targeting assessment for patients treated with hypofractionated radiation therapy and ADT.

Voxel level dose distribution, normal tissue complication, and tumor control will be collected. All images will be co-registered and normalized. Functional principal component analysis will be used to develop dose response and tumor control models.

8.2.4 To explore the changes in serum levels of inflammatory and angiogenic cytokines as biomarkers of treatment response, we will use Bioplex 200 technology to batch analyze a 27 cytokine panel in parallel at baseline and after 3 and 24 months of completing treatment. The blood collected in one 8 ml serum separation tube (BD vacutainer, lavender-top) will be allowed to stand 45-60 minutes and processed within one hour. The tube will be centrifuged at 1200g for 10 min in a swing out rotor (approximately 2500rpm). The serum will be transferred into a clean empty 15ml tube using Pasteur pipette. The serum will be aliquoted into 1.05 ml volume in each cryopreservation vial and stored in -80°C or -20°C freezer. We will process the samples as described previously by our Co-I [name]. Briefly, The Bioplex 200 (Bio-Rad, Hercules, CA) platform will be used to determine the absolute concentration (in pg/ml) of 27 target proteins in banked sera samples. A multiplexed bead-based immunoassay is performed in duplicate for each serum sample following the manufacturer's protocols and using the supplied cytokine standards. The concentration of each cytokine will be determined using a 5-parameter log curve fit using the supplied software. The Human 27-plex panel includes validated assays for IL-1b, IL-1ra, IL-2, IL-4, IL-5, IL-6, IL-7, IL-8, IL-9, IL-10, IL-12(p70), IL-13, IL-15, IL-17, eotaxin, basic FGF, G-CSF, GM-CSF, IFNg, IP-10, MCP-1, MIP1a, MIP1b, PDGF-BB, vascular endothelial growth factor (VEGF), and TNFa. This data will be correlated with primary and other secondary objectives.

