5.0 RADIATION THERAPY AND RESEARCH INTERVENTIONS

Rather than receiving combined 40 fractions of radiation over 8 weeks and 4 months of ADT, patients enrolling on the study will receive combined radiation in 5 fractions over 2 weeks and 4 months of ADT (≥ 1 month prior to radiation therapy). There will be no alteration in what patients experience in a treatment session other than a longer (estimated at 2-3 minutes for VMAT and 30 minutes for CyberKnife) duration of beam-on time. A schema of the treatment plan is presented below:

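### Does the 5-year BFFR need a stated time origin and a rule for the Year-5 PSA before it can be read from the Kaplan-Meier curve?

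*Combined protocol and SAP*

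**What the plan says.** - Section 8.1 defines BFFR as a yes/no indicator of a PSA at nadir + 2 ng/ml within five years. It fits a Kaplan-Meier curve with Greenwood variance, "then estimating the 5-year biochemical failure free rate (BFFR) from this K-M curve together with 95% confidence interval". It does not say when the five years begin, when a failure-free patient is censored, or how the Year-5 PSA enters.
- Section 6.2.2, repeated in calendar footnote 11: "Time of failure will be the date of the first PSA that is 2 ng/ml or more above the nadir". After a rise above 25% and of at least 0.3 ng/ml, the patient "will have PSA drawn every 3 months until PSA either returns to nadir value" or reaches the failure threshold.
- Section 6.2.1: visits are 6-monthly to year 3, "then annually until year 5. The patient will be off study after 5 years".
- Section 7.0: the follow-up columns are "in time post radiation treatment", and under footnote 16 "all other follow-up appointments have a +/- 30 day tolerance window".
- Section 8.2.2: "Disease-Free Survival, measured from the date of enrollment to the date of documented progression"; time to local progression, time to distant failure and overall survival start at the same date.
- Section 8.3: expected BFFR of 85% or more, at least five years of follow-up for everyone, a 95% interval narrower than 0.14 with 100 completers, and 110 patients in total.

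**The concern.** The only primary estimate is a single point on a curve, read close to the time at which nearly every patient has a last PSA. Failure carries its actual date, and the Year-5 visit may fall 30 days either side of its due date. A literal reading at month 60 therefore includes some Year-5 results and omits others.

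The origin looks worse. The secondary survival endpoints run from enrollment. If BFFR did too, and enrollment came more than 30 days before the end of radiation, every in-window Year-5 PSA would fall after month 60 and be left out. Two analysts could then report different primary results from the same data, and most of the plausible differences favour the regimen.

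**Working it through.** **1. The plan's own figure.** With 100 completers at 85% (section 8.3), the width is 2 × 1.96 × √(0.85 × 0.15 / 100) = 0.140. This reproduces the plan. The standard error is about 3.6 points and the half-width 7 points.

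**2. How much the last year holds.** Assume a constant hazard. Then S(4 years) = 0.85^(48/60) = 0.878, and the conditional failure probability for year 4 to 5 is q = 1 − 0.85^(12/60) = 0.032. The product is 0.878 × 0.032 = 0.028. Omitting every failure of that year would raise the estimate by 2.8 points.

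**3. End-of-radiation clock, scheduled PSAs only.** Suppose a fraction f of Year-5 PSAs falls before month 60 and failure-free patients are censored at their last PSA. The curve then counts about −ln(1 − f) × q instead of q.

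| f | 0 | 0.25 | 0.50 | 0.63 | 0.75 | 0.90 |
|---|---|---|---|---|---|---|
| Shift (points) | +2.8 | +2.0 | +0.9 | about 0 | −1.0 | −3.4 |

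Even scatter means f = 0.5: 0.878 × exp(−0.032 × 0.693) = 0.859. Simulating 3,000 trials of 110 patients also gives +0.9, with a mean Greenwood standard error of 3.5 points.

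**4. Adding the triggered PSAs of section 6.2.2.** The documents give no PSA kinetics, so doubling times of 3 to 12 months and nadirs of 0.1 and 0.4 ng/ml are assumed. Of 110 × 0.15 = 16.5 expected failures, 3.10 are first found in the Year-5 window without triggers and 0.74 to 1.69 with them. The triggers thus recover (3.10 − 1.69)/3.10 = 45% to (3.10 − 0.74)/3.10 = 76%. With even scatter the shift falls to between about −0.2 and +0.6 points. Simply assuming that 50% or 90% of failures are caught between visits gives +0.45 or +0.13.

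**5. Enrollment clock.** Section 5.0 gives at least 1 month of ADT before radiation and 2 weeks of radiation. If ADT starts on study, the lag is about 1.5 months, longer than 30 days (0.986 month), so f = 0.
- Scheduled PSAs only: +2.8 points against the radiation-clock value.
- With triggers, under the kinetics in step 4: about +0.4 to +1.5.
- With a flat 50% caught between visits: +1.8.

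The standard error in the simulated enrollment-clock cases is about 3.2 points. The lag is itself an assumption: section 6.1 allows for patients who began ADT before consenting to the optional blood samples, which could shorten it.

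**6. Downward shifts.** These need failure-free patients to be censored at their last PSA and most visits to be early. With all visits before month 60, scheduled PSAs only, the mean shift is −10.4 points (SD 17); with triggers it is −1.5 to −5.8. If failure-free patients instead stay at risk to month 60, the curve counts f × q:
- f = 0.5: 0.878 × (1 − 0.016) = 0.864, a shift of +1.4.
- f = 0.75: 0.878 × (1 − 0.024) = 0.857, a shift of +0.7.
- All visits early: +0.2 by simulation.

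The marked falls disappear.

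**7. What an explicit mapping rule would gain.** Placing in-window Year-5 PSAs at month 60 on an end-of-radiation clock gives 0.846 to 0.851 in every setting tried. Under the natural reading with even scatter, the error would go from between −0.07 and +0.62 to between −0.14 and +0.08, a gain of about half a point. If all visits run late, the mapped estimate reads up to about 0.4 points low. Counting failures to month 61 explains at most 0.23 of that, since 0.85^(61/60) = 0.8477. Reading the actual-date curve at month 61 instead is worse (median −4.9 points), because the risk set runs out.

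**The case for a change.** The strongest case for a change is that a primary estimate should be reproducible from its own text. The plan names an origin for four secondary endpoints and none for the primary. Patients leave the study after Year 5, so no later scheduled PSA can replace one that was left out. A rule chosen after the data are seen cannot be shown to be neutral, and a sentence in 8.1 would cost no visits or patients.

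Part of this stands. The text is silent on origin, censoring and the Year-5 PSA. The origin matters more than visit scatter: on an enrollment clock the shift can exceed 1 point and is upward. The reassurance from triggered PSAs depends on kinetics that the documents do not give.

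The rest is weaker. The larger upward figures need an enrollment clock that the visit calendar does not use, or no triggered draws although 6.2.2 requires them, or visits that mostly run late. The large downward figures need nearly all Year-5 visits to be early, which fits poorly with the five-year follow-up promised in 8.3 and would show in the number at risk. A mapping rule would also override the failure date fixed in 6.2.2 and footnote 11, so one PSA failure could carry different dates for BFFR and for disease-free survival. Which origin is best is itself open to debate.

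**Conclusion.** This is missing detail that an analyst would fill sensibly. The calendar counts from radiation, the endpoint is a five-year yes/no status, and follow-up ends with the Year-5 visit. Together these point to an end-of-radiation clock on which the Year-5 PSA settles that status. On that reading, even reading strictly by actual date moves the estimate by about half a point, against a standard error near 3.5 points and a planned half-width of 7. The enrollment alternative adds roughly 0.4 to 1.5 points with triggered PSAs, and its bound of 2.8 is still below one standard error.

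The sizes rest on a true BFFR of 85%, constant hazard, the assumed PSA kinetics, even visit scatter and, for the enrollment clock, a lag of more than 30 days. If hazard rises with time or visits run late, the scheduled-only shifts grow (+1.7 points, or +2.8 with visits 15 days late on average) but stay below one standard error. N, the planned interval width and the stopping rules do not depend on the choice, since the latter concern toxicity and BFFR has no success threshold. No change to the plan follows.
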